8.1.4. Time Period for Collecting AE/SAE Information

The time period for actively eliciting and collecting AEs and SAEs (“active collection period”) for each subject begins from the time the subject provides informed consent, which is obtained before the subject’s participation in the study (ie, before undergoing any study-related procedure and/or receiving investigational product), through and including a minimum of 30 calendar days; except as indicated below after the last administration of the investigational product.

If a patient begins a new anticancer therapy, the recording period for all AEs ends at the time the new treatment is started. However, the reporting of SAEs should continue beyond this period if the investigator believes there to be at least a reasonable possibility of the SAE being related to investigational product. Phone patients for follow up if they do not come to the clinic within the follow up period.

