5. Must be within 42 days before randomization. Screening includes posteroanterior and lateral chest x-ray or chest CT scan, whole-body radionuclide bone scan, and abdominopelvic CT/MRI. If the screening bone scan shows a lesion suggestive of metastatic disease, the patient will be eligible only if a second imaging modality (plain film, CT, or MRI) excludes bone metastasis. If the imaging results are equivocal or consistent with metastasis, the patient is not eligible for enrollment. Use the same imaging method throughout the study.
6. Perform approximately every 16 weeks, but obtain images sooner if progression is clinically suspected. Radiographic imaging should be performed until radiographic progression is identified and confirmed by independent central radiology review per protocol. A second imaging modality (plain film, CT, or MRI) confirmation of bone progression is required when bone lesions are found in a single region on the bone scan.
7. If disease progression is suspected, perform imaging studies as appropriate.
8. Complete, sign, and fax the randomization authorization form to the medical monitor at the number provided on the form at least 2 business days before the day 1 visit.
9. Assess systems per standard of care at the study site and as clinically indicated by symptoms. Includes assessment of vital signs and weight (height only at screening).
10. Symptom directed and includes investigating any new abnormalities and assessment of vital signs.
11. Questionnaires will be completed for patients who come to the clinic.
12. Collect nonserious adverse event information from the time of first dose of study drug through safety follow-up. If no safety follow-up, collect adverse event information through 30 days after the last dose of study drug. Phone patients for follow-up if they do not come to the clinic.
13. May obtain at clinic visits, by phone contact, chart review, etc. Includes survival status, new antineoplastic therapies for prostate cancer, opiate use, skeletal-related events, and interventions due to locoregional progression.
14. Refer to the laboratory instruction manual for sample processing.

Study Period or Visit	Screening	Treatment			Unscheduled	Safety FU	Long-Term FU
Study Week	-4 to -1	1	5	17 Then Every 16	Varies [1]	Varies [2]	Every 16
Study Day	-28 to -1	1	29	113	na	na	na
Window (Days) [3]	na	na	±5	±5	na	±7	±7

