BPI-SF, Brief Pain Inventory Short Form; CT, computed tomography; ECOG, Eastern Cooperative Oncology Group; EQ-5D-5L, European Quality of Life-5 Dimensions-5 Levels health questionnaire; FACT-P, Functional Assessment of Cancer Therapy-Prostate; FU, follow-up; IXRS, interactive voice/web recognition system; MRI, magnetic resonance imaging; na, not applicable; opt, optional; QLQ-PR25, Quality of Life Questionnaire-Prostate 25.

Supplement 1: Open-Label Period

NOTE: This supplement contains cross-references to the main protocol text where study procedures are to be performed in the same manner.

Rationale: As the study met the primary efficacy endpoint of metastasis-free survival and the established safety profile of enzalutamide was confirmed all patients will be unblinded. Eligible patients will receive enzalutamide at the discretion of the investigator. For patients that have not progressed radiographically, scans (CT/MRI and bone scan) will be performed per investigator discretion until patient has progressed radiographically. Continuation of treatment on the open-label period after radiographic progression will at the discretion of the investigator. Patients who do not participate in the open-label period or withdraw consent for further treatment will continue long-term follow-up assessments per protocol. Treatment with open-labeled Enzalutamide will be stopped upon disease progression when in the opinion of the Investigator, there is no added clinical benefit to continue treatment with Enzalutamide.

Long-term follow-up data (Includes survival status, new antineoplastic therapies for prostate cancer, skeletal-related events, and interventions due to locoregional progression) will be collected every 16 weeks.

Day 1 of the open-label period will occur after consent is signed and eligibility for all patients is verified. Patients who choose not to continue in the open-label period will discontinue treatment and return for safety follow-up within approximately 30 days after last dose.

Sites must have all open-label day 1 visits completed within 16 weeks after IRB/EC approval of this protocol amendment.

Patients who will receive any other treatment for prostate cancer after unblinding, will not be eligible for an open label enzalutamide extension.

Schedule and Assessments:

For procedures see [Supplement Table 1: Study Schedule of Activities \(Open-Label Period\)](#).

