2. For patients previously receiving placebo, open label day 1, week 1, must be within 16 weeks after the approval and activation of this protocol at the study site and no later than 16 weeks after screening. For patients continuing treatment with enzalutamide, open label day 1 will be their next regular scheduled visit following approval and activation of this protocol at the study site.
3. Only for patients starting new treatment with enzalutamide (previously received placebo).
4. Anytime necessary to assess or follow up adverse events, at the patient's request, or per investigator decision.
5. Approximately 30 days after the last dose of study drug. If a new antineoplastic treatment is initiated before 30 days after the last dose of study drug, then safety follow up will occur immediately before starting the new treatment.
6. Drug supply must be taken into account if a window is used to schedule the next visit. Visits may be split across the window to allow for drug resupply and completion of study procedures.
7. Must obtain informed consent before performing any study specific procedures at screening for patients starting new treatment with enzalutamide and on day 1 for all patients continuing treatment with enzalutamide.
8. Only for patients continuing enzalutamide treatment.
9. When the investigator determines a patient is eligible, study site personnel will complete and email this form to the e-mail address provided on the form. The sponsor medical monitor will approve the enrollment in writing or contact the study site. No form is required for patients continuing enzalutamide treatment.
10. Read locally.
11. Symptom directed and includes investigating any new abnormalities and assessment of vital signs.
12. For patients that have not progressed radiographically, scans (CT/MRI and bone scan) will be performed per investigator discretion until patient has progressed radiographically.
13. Collect nonserious adverse event information from the time of signing of informed consent through safety follow up. Collect and report serious adverse event information from the time of signed informed consent through screen failure or safety follow up. If no safety follow up, collect adverse event information through 30 days after the last dose of study drug. Phone patients for follow up if they do not come to the clinic.

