7. DEFINITIONS, COMPUTATIONS, AND CONVENTIONS

7.1. Definitions and Computations

Study Day

Study day will be calculated in reference to the date of randomization (Study Day 1). For assessments conducted on or after the randomization date, study day is calculated as (assessment date – randomization date + 1). For assessments conducted before the randomization date, study day is calculated as (assessment date – randomization date). There will be no Study Day 0.

Date of First Dose and Date of Last Dose of Study Drug

The date of the first dose of study drug is defined as the date a patient receives the first dose of study drug (enzalutamide or placebo). The date of the last dose of study drug is defined as the date a patient receives the last dose of study drug (enzalutamide or placebo).

Treatment Day

Treatment day will be calculated in reference to the date of the first dose of study drug. Treatment Day 1 corresponds to the date a patient receives the first dose of study drug. For assessments conducted on or after the date of the first dose of study drug, treatment day will be calculated as (assessment date – date of first dose of study drug + 1). There will be no Treatment Day 0.

Treatment Period

The treatment period is defined as the period of time from the date and time of the first dose of study drug through the date of last dose.

Treatment-Emergent Period

The treatment-emergent period is defined as the period of time from the date and time of the first dose of study drug through the date of last dose + 30 days (or the day before initiation of a new antineoplastic treatment, whichever occurs first).

Treatment Duration

Treatment duration is defined as the duration of time from the date of the first dose of study drug to the date of the last dose of study drug as follows:

Treatment Duration (days) = Date of last dose of study drug – Date of first dose of study drug + 1.

Treatment Duration (months) = (Date of last dose of study drug – Date of first dose of study drug + 1)/30.4375.

Long-Term Follow-up Period

The long-term follow-up period will start the day after the last day of study drug treatment and will continue through the data cutoff date.

Baseline Value and Postbaseline Value

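### Schedule notes let adverse-event collection stop at a safety visit as early as day 23, while Protocol 8.1.4 requires at least 30 days and the SAP counts the full 30

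*Protocol*

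**What the plan says.** **Section 8.1.4 (controlling text).** The active collection period for adverse events, serious and nonserious, "begins from the time the subject provides informed consent" and runs "through and including a minimum of 30 calendar days" after the last administration. Recording of adverse events stops earlier only when a new anticancer therapy starts.

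**Schedule instructions.** Three places end collection at the safety follow-up:
- Appendix 5 note 12, nonserious events: "Collect nonserious adverse event information from the time of first dose of study drug through safety follow-up".
- Supplement Table 1 note 13, nonserious events: "Collect nonserious adverse event information from the time of signing of informed consent through safety follow up". Serious events: "Collect and report serious adverse event information from the time of signed informed consent through screen failure or safety follow up".
- Protocol Table 1 (screening procedures) gives the same endpoint for serious events in the double-blind period.

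Note 12 adds a fallback: "If no safety follow-up, collect adverse event information through 30 days after the last dose of study drug". Note 13 has the equivalent sentence.

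**Timing of the visit.** Section 5.4.1, Appendix 5 note 2, the Supplement 1 schedule text and Supplement Table 1 note 5 place it about 30 days after the last dose. Both schedules allow plus or minus 7 days. For men who do not enter the open-label period, the Synopsis and the Supplement 1 rationale say they "return for safety follow-up within approximately 30 days after last dose".

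**SAP.** Section 7.1 defines the treatment-emergent period as "from the date and time of the first dose of study drug through the date of last dose + 30 days", cut short by a new antineoplastic treatment. Section 9.8.1 counts events that start or worsen in that period and divides occurrences by patient-years of treatment-emergent surveillance.

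**The concern.** A site working from the schedule can stop asking about adverse events on day 23 and be compliant with the note it is reading, while Section 8.1.4 still requires collection for another week. The fallback makes this odder: a man who misses the visit is followed to day 30, and a man who attends on day 23 is not. It also suggests that 30 days was intended throughout.

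The SAP treats every day to last dose plus 30 as observed. An event on day 26 in a man seen on day 23 may never be elicited, yet day 26 stays in the denominator of the time-adjusted rate. The error can only go towards undercounting.

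The boundary has a second use. Section 8.3.3 makes reporting of fatal disease progression as a serious event depend on whether the death falls in the active collection period, so that period should have one meaning.

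**Working it through.** The plan states no figure for this point, so there is nothing to reproduce. The check compares the windows and then sizes the gap.

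**Step 1: windows side by side**

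| Source | Events covered | End of collection or counting |
|---|---|---|
| Protocol 8.1.4 | Serious and nonserious | At least 30 calendar days after last dose; adverse-event recording ends earlier if new anticancer therapy starts |
| Appendix 5 note 12 | Nonserious | Safety follow-up; day 30 only if there is none |
| Supplement Table 1 note 13 | Serious and nonserious | Safety follow-up; day 30 only if there is none |
| Protocol Table 1 | Serious | Screen failure or safety follow-up |
| SAP 7.1 and 9.8.1 | Treatment-emergent events and patient-years | Last dose + 30 days, or the day before new antineoplastic treatment |

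**Step 2: is there a later contact?** Section 5.4.1, Section 8.1.4 and notes 12 and 13 provide for telephone contact with men who refuse or do not attend clinic visits. Nothing requires a further contact on day 30 for a man already seen on days 23 to 29.

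**Step 3: size of the gap per patient.** Earliest visit in the window: 30 − 7 = day 23. Latest: 30 + 7 = day 37. Gap = max(0, 30 − visit day).

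| Visit day | Gap (days) | Share of the 30 days |
|---|---|---|
| 23 | 7 | 23.3% |
| 25 | 5 | 16.7% |
| 27 | 3 | 10.0% |
| 29 | 1 | 3.3% |
| 30 to 37 | 0 | 0% |

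If visits were spread evenly over days 23 to 37 (an assumption), 7 of 15 visit days (47%) would leave a gap. The mean gap would be (7 + 6 + 5 + 4 + 3 + 2 + 1)/15 = 28/15 = 1.9 days.

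**Step 4: share of person-time.** Share = gap / (treatment months × 30.4375 + 30), using the SAP 7.2 month length. Treatment durations are assumptions; the gap is set at its maximum of 7 days.

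| Assumed treatment | Treatment-emergent days | Maximum share |
|---|---|---|
| 3 months | 121.3 | 5.8% |
| 6 months | 212.6 | 3.3% |
| 12 months | 395.3 | 1.8% |
| 24 months | 760.5 | 0.9% |
| 33 months | 1034.4 | 0.7% |

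With the mean gap of 1.9 days, the share is 1.5% at 3 months and 0.5% at 12 months. As an absolute ceiling, if all 1440 men had day-23 visits, the unsurveyed time would be 1440 × 7/365.25 = 27.6 patient-years.

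**Step 5: after the fix.** If collection runs to at least day 30 whatever the visit day, the gap is 0.

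**The case against.** The strongest reply is that Section 8.1.4 governs and already requires 30 days, so this is a loose footnote. On that view, safety follow-up may mean a period and not a visit: SAP Section 2 lists it among the study periods, and SAP Table 1 spans it from last dose to last dose plus 30. Under that reading the notes agree with 8.1.4. It is possible, but the fallback sentence for men with no safety follow-up fits a visit better than a period. The text is at best ambiguous, and a site should not have to resolve it.

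A second reply is that the window is symmetric, so late visits offset early ones. They do not: events after day 30 lie outside the SAP's treatment-emergent period and cannot replace those missed before it.

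Other objections stand and limit the point:
- **New therapy.** When the visit is early because a new anticancer treatment is starting, Section 8.1.4 and the SAP stop too. There is essentially no conflict.
- **Serious events.** A reader might infer that serious events in the gap reach the sponsor only if the investigator happens to learn of them. Section 8.1.4.1 says that only of events after the active collection period. Days 23 to 30 lie inside that period, and all serious events in it are to be reported.
- **Much earlier visits.** For men declining open label, a reader might take "return for safety follow-up within approximately 30 days after last dose" to permit a visit on, say, day 7, losing 23 of 30 days (77%). That rests on one loose phrase against Section 5.4.1, both schedules and the Supplement 1 text, all of which place the visit at about day 30.
- **Start of collection.** Section 8.1.4 starts at consent and note 12 at first dose. This does not change treatment-emergent counts, which begin at first dose, and Protocol Table 2 sends new day-1 events to the medical history form.
- **Comparison of arms.** Nothing in the documents shows that early visits would differ by arm.

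**Conclusion.** The contradiction is in the current text. Section 8.1.4 requires at least 30 calendar days, while three schedule instructions allow collection to end at a visit that may fall on day 23. The SAP counts the missing days as surveyed.

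The supported gap is at most 7 of 30 post-dose days (23%). As an understatement of time-adjusted rates it is small: at most 1.8% at 12 months of treatment and 0.9% at 24 months, rising to 5.8% at 3 months. These figures assume the stated durations, a day-23 visit, no collection after it and an event rate that is constant over the treatment-emergent period. A site that follows Section 8.1.4 loses nothing. The exposure is mainly to nonserious events, and the documents do not support a claim of between-arm bias or of losses beyond 7 days.

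The point should be corrected because the remedy is cheap and closes a real gap in safety data. It does not threaten the trial's safety conclusions.

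**What to change.** 1. Amend Protocol Table 1, Appendix 5 note 12 and Supplement Table 1 note 13 so that each follows Section 8.1.4: collection continues through at least 30 calendar days after the last dose, or until new anticancer therapy starts. Leaving out Table 1 would keep the serious-event endpoint in conflict.
2. Add a telephone contact on or after day 30 for any man whose safety visit falls earlier and who has not started new therapy.
3. In the Synopsis and the Supplement 1 rationale, align the visit timing for men not entering open label with Section 5.4.1 and the Supplement 1 schedule text, which place it about 30 days after the last dose.

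The cost is a few wording changes and one call per early visit, using a contact method that the notes already provide. The Synopsis says that the double-blind period has concluded, so correcting Table 1 and note 12 is largely for consistency. The prospective gain is for open-label patients and men leaving treatment.

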Patients previously receiving enzalutamide will sign informed consent on open-label day 1 (their next regular scheduled visit following approval and activation of this protocol at the study site) and have clinic visits whenever clinically indicated or needed. Patients previously receiving placebo will sign informed consent at screening and have clinic visits on open-label day 1, week 5, week 17, and every 16 weeks thereafter. All patients must have their open-label day 1 visit within 16 weeks after the approval and activation of this protocol at the study site and no later than 6 weeks after screening (for placebo patients only). The enrollment period will end after this time.

Patients will take enzalutamide as four 40-mg soft gelatin capsules (160 mg/day) by mouth once daily with or without food.

Study assessments will include survival status, new prostate cancer therapies, and safety evaluations including adverse events, concomitant medications, clinical laboratory tests, brief physical examinations, screening electrocardiograms (ECGs), and vital signs. For patients that have not progressed radiographically, scans (CT/MRI and bone scan) will be performed per investigator discretion until patient has progressed radiographically by local determination.

[figure not shown]
At a minimum, the following laboratory values from those listed in protocol [Section 8.6](#) must be evaluated at screening (for placebo patients) and throughout the study locally:

- **Hematology:** hematocrit, hemoglobin, platelet count, red blood cell count, white blood cell count with differential, and absolute neutrophil count must be obtained or be able to be calculated.
- **Comprehensive chemistry panel:** albumin, alkaline phosphatase, ALT (alanine aminotransferase), AST (aspartate aminotransferase), creatinine, blood urea nitrogen (BUN) or urea, Ca⁺⁺, total CO₂ (bicarbonate), glucose, Na⁺, K⁺, Cl⁻, total bilirubin.

Patients are to have a safety follow-up approximately 30 days after the last dose of open-label enzalutamide. If a new antineoplastic or investigational anticancer treatment is initiated before 30 days after the last dose, then safety follow-up should occur immediately before starting the new treatment.

Long-term follow-up data will be collected every 16 weeks. The information collected will include survival status, new antineoplastic therapies for prostate cancer, skeletal-related events, and interventions due to locoregional progression.

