Safety will be evaluated by the frequency of serious adverse events, frequency and severity of adverse events, frequency of study drug discontinuation due to adverse events, and frequency of new clinically significant changes in clinical laboratory values and vital signs.

All adverse events will be coded to preferred term and system organ class using the Medical Dictionary for Regulatory Activities (MedDRA). The number and percentage of patients with adverse events will be presented by MedDRA system organ class and preferred term, relationship to study treatment, and severity. Descriptive statistics will be used.

Central laboratory values (from the double-blind portion study) will be classified for severity using the National Cancer Institute Common Terminology Criteria for Adverse Events (CTCAE), version 4. Descriptive statistics will be used to analyze the laboratory data.

Supplement Table 1: Study Schedule of Activities (Open-Label Period)

Study Period or Visit Study Week Window (Days) [6]	OL Screen [1]	Treatment			Unscheduled	Safety FU	Long Term FU
	na	OL 1 [2]	OL 5 [3]	OL 17 Then Every 16	Varies [4]	Varies [5]	Every 16
	na	na	±5	±5	na	±7	±7
General Activities							
Informed consent [7]	X	X [8]					
Eligibility criteria for OLE	X						
Enrollment Authorization Form [9]	X						
12 Lead electrocardiogram [10]	X						
Brief physical examination [11]	X	X		X	X	X	
Radiographic assessments [12]				X	X		X
Serious and non-serious adverse event monitoring [13]	X		X [3]	X	X	X	
Concomitant medications review	X	X	X [3]	X	X	X	
Dispense enzalutamide (via IWRS)		X		X			
Study drug accountability			X [3]	X		X	
Local laboratory evaluation [14]	X	X		X	X (optional)	X	
Long Tern Follow-up Assessments[15]		X [8]					X

1. Only for patients starting new treatment with enzalutamide (previously received placebo). Qualifying patients continuing treatment with enzalutamide may proceed to open label day 1 procedures. The investigator will assess and confirm patient eligibility for open label extension. All screening procedure results and relevant medical history must be available to determine eligibility. All inclusion criteria must be met and no exclusion criteria may apply. No eligibility waivers will be granted.

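### No blood pressure is scheduled at open-label week 5, so former placebo patients who stay on enzalutamide have their first on-drug reading at week 17

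*Protocol*

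**What the plan says.** Supplement 1 to the protocol sends sites to one table for open-label procedures: "For procedures see [Supplement Table 1: Study Schedule of Activities". The clinic visits for patients coming off placebo are set out in the text: "Patients previously receiving placebo will sign informed consent at screening and have clinic visits on open-label day 1, week 5, week 17", then every 16 weeks. Note 3 to the table restricts the week 5 visit to these patients: "Only for patients starting new treatment with enzalutamide (previously received placebo".

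The table has no separate row for vital signs. They sit inside the row "Brief physical examination [11]", because note 11 describes that examination as "Symptom directed and includes investigating any new abnormalities and assessment of vital signs". The row is marked at open-label screening, day 1, week 17 and every 16 weeks after, unscheduled visits and safety follow-up. It is blank at week 5. Three other rows are marked at week 5 for new starters: "Serious and non-serious adverse event monitoring [13]", concomitant medications and drug accountability.

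The supplement's text includes "brief physical examinations, screening electrocardiograms (ECGs), and vital signs" among the open-label assessments but ties vital signs to no visit. Its Statistical Methods section counts "frequency of new clinically significant changes in clinical laboratory values and vital signs" among the safety measures.

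**The concern.** Former placebo patients are as new to enzalutamide on open-label day 1 as the enzalutamide arm was on double-blind day 1, yet they get less early monitoring of blood pressure. The double-blind week 5 visit (Section 5.2.4, Table 3, and Appendix 5) measures it; the open-label week 5 visit does not, and the supplement gives no reason for the difference.

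The protocol itself makes blood pressure worth measuring early. Section 1.4 lists hypertension as an important identified risk. Section 1.2 lists it among reactions seen in at least 10% of enzalutamide patients, and at least 2% more often than on placebo, in the two placebo-controlled phase 3 studies. SAP Section 9.8.1.1 makes it an adverse event of special interest. Section 1.2.1 says steady state takes about 1 month, so week 5 is the first visit near full exposure. Asking about adverse events at week 5 will not detect a rise that causes no symptoms.

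**Working it through.** **Step 1: where each schedule takes vital signs after enzalutamide starts.** Section 8.7 defines vital signs as blood pressure, heart rate and temperature.

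| Visit | Double-blind (Appendix 5; Table 3 for week 5) | Open-label, former placebo (Supplement Table 1) |
|---|---|---|
| Day 1 | Marked (baseline) | Marked (baseline) |
| Week 5 | Marked | Blank |
| Week 17, then every 16 weeks | Marked | Marked |

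Open-label day 1 counts as baseline because enzalutamide is first dispensed at that visit and next at week 17.

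**Step 2: is the blank real, or a fault in reading the table?** The concomitant medications row fills every column from screening to safety follow-up in order, with the week 5 entry carrying note 3. The adverse event row is blank at day 1 and carries note 3 at week 5. The laboratory row shows its optional mark under unscheduled visits. The columns line up across rows, so the blank is in the plan.

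**Step 3: does other text fill the gap?** The supplement's list of assessments gives no visit for vital signs. Section 8.7 points to Appendix 5, which is the double-blind schedule. No open-label text brings Table 3 into the open-label week 5 visit.

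**Step 4: the delay.** Visit day = (week − 1) × 7 + 1, which reproduces days 29 and 113 in Appendix 5.

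- Week 5: (5 − 1) × 7 + 1 = day 29; with ±5 days, 24 to 34.
- Week 17: (17 − 1) × 7 + 1 = day 113; with ±5 days, 108 to 118.
- Nominal delay: 113 − 29 = 84 days (12 weeks).
- Shortest: 108 − 34 = 74 days. Longest: 118 − 24 = 94 days.

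**Step 5: what cannot be computed.** The documents do not give the number of former placebo patients entering the open-label period, or the share of hypertension that begins before week 17. The 10% and 2% thresholds cover the whole of treatment in metastatic disease. No case count follows from them.

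**Step 6: is anything else missing at week 5?** Laboratory tests are also blank there, but the double-blind week 5 visit had none either. ECOG status was assessed at double-blind week 5, but it has no row anywhere in the open-label table. Of the safety checks the open-label table keeps, only the brief examination with its vital signs was dropped at this visit.

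**The case against.** The strongest reply is that this is a permissible design choice. Nothing in the supplement requires vital signs at week 5, so there is no internal contradiction. The open-label period follows unblinding, on the stated ground that the drug's safety profile was confirmed, and monitoring is lighter throughout: PSA, ECOG status and questionnaires have no row, laboratory tests become local, and scans are left to the investigator. There are partial safeguards. Vital signs can be taken at unscheduled visits; open-label exclusion 4 keeps out former placebo patients with a clinically significant cardiovascular disorder that may interfere with participation; there are two pre-treatment readings; and adverse events and new medications, including antihypertensives, are reviewed at week 5. The harm is not quantified, and no passage links the onset of raised blood pressure to steady state. Finally, a one-cell change may need an amendment approved by ethics committees across about 250 centers, and could come too late for many week 5 visits.

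Much of this stands as context. It narrows the consequence to an unrecognised, symptomless rise between day 1 and week 17, and it shows that the schedule is lighter rather than contradictory. It does not supply a scheduled on-drug reading. Unscheduled visits need a prompt, and exclusion 4 acts before treatment starts. A wish to reduce burden explains little here, because these patients attend clinic at week 5 anyway. The timing point is fair: the protocol describes the open-label period as ongoing, so the change helps only patients who have not yet passed week 5.

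**Conclusion.** The concern holds. For former placebo patients who stay on enzalutamide, the first scheduled on-drug blood pressure is at about day 113 instead of day 29: 84 days later, or 74 to 94 days across the visit windows. This rests on two readings of the protocol: that Supplement Table 1 governs open-label procedures, and that the day 1 measurement is a baseline. It concerns scheduled readings only. Patients who stop early are measured at safety follow-up, about 30 days after the last dose, and unscheduled visits may give earlier readings in others.

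The point is minor. It does not touch the efficacy analyses, and the 84 days is a scheduling interval, not a count of missed events. It is still worth correcting, because the risk is one the protocol itself identifies, it can be silent, and the remedy is cheap.

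**What to change.** In Supplement Table 1, mark the brief physical examination at open-label week 5 with note 3, so that new starters have vital signs taken then, as at the double-blind week 5 visit in Table 3. The first scheduled on-drug blood pressure then returns to day 29 (±5 days).

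For the patient this means a short examination at a clinic visit already in the schedule, with no extra visit or blood test. For the sponsor it is one table cell if made before the amendment is approved. Afterwards it should go into the next amendment, and would benefit only those who have not yet reached week 5.
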